#### 10.2.12 Handling of Missing Data for Adverse Events

For the analysis of AEs, the following assumptions will be applied.

- If the AE severity is missing, it will be assumed that the AE was severe.
- If the AE relationship is missing, it will be assumed that the AE was definitely related to study drug.

### 10.2.13 Handling of Immunogenicity Data for the Second and Third Study Drug Exposure

#### **Combined Visits**

In case of combined study visits according to scheduled visit dataset, immunogenicity data supporting two combined visits will be programmatically copied to both visits.

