4.1.3.2 Subsequent Icatibant-Treated Attacks

Subsequent treatment with icatibant may be offered to pubertal/postpubertal subjects who have received initial treatment and who present subsequently with an attack at least 3 days after prior treatment. Subjects will be eligible for treatment with icatibant until a total number of at least 10 adolescents have been treated 3 times with icatibant.

For all subjects who remain enrolled in the study for longer than 6 months, a study visit will be scheduled every 6 months to collect baseline information and to conduct training for parents/legal guardian/caretakers for subjects who have expressed an interest in receiving icatibant at home. In addition, for all subjects who remain enrolled in the study a safety telephone contact will be scheduled every month to collect information concerning AEs, weight, eligibility, and HAE attacks not treated within the study.

When a pubertal/postpubertal subject experiences an acute HAE attack, subjects (parent/legal guardian/caregiver) will contact the hospital/study center (or their home healthcare professional in the event the investigator is not available) to confirm the HAE attack diagnosis.

The investigator (or the home healthcare professional in the event the investigator is not available), in consultation with the subject's preference, will determine whether the subject will be treated at the hospital/study center, at home by a qualified home healthcare personnel, or at home by the trained parent/legal guardian/caregiver. The qualified home healthcare person will be contacted, if applicable.

For subsequent attacks, study drug may be administered by study site personnel at the hospital/study center or by qualified home healthcare personnel at the subject's home. Alternatively, a parent/legal guardian/caregiver will be allowed to administer or the subject (under the supervision of a parent/legal guardian/caregiver) will be allowed to self-administer the investigational product after having received appropriate training. For all subsequent laryngeal attacks, subjects should be advised to seek medical attention in an appropriate healthcare facility immediately following treatment with icatibant.

Except for PK determinations, all primary and secondary endpoints are to be measured after each administration. Safety, reproductive hormones, and other assessments in association with

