4.3 Study Duration

At minimum, the duration of a subject's active participation in the study will consist of single day dosing with 90-day follow-up.

Once eligibility is established at screening, the subject will be enrolled into the study but will enter a period of inactive participation of variable duration until such time as the subject experiences an acute attack of HAE and is offered treatment. For those pubertal/postpubertal subjects who will be treated without an attack, eligibility will be established at screening and the subject will be immediately enrolled and treated with icatibant. At the time of enrollment, the subject will enter a 90-day period of active participation which will consist of treatment with a single SC administration of icatibant on Day 1 through follow-up at Day 90.

After receiving the first treatment with icatibant with or without an attack (N=20), at least 10 pubertal/postpubertal subjects who present with subsequent attacks of acute HAE will continue to receive treatment with icatibant for a total of 3 attacks each. Thus, the period of active participation in the study for prepubertal subjects could be approximately 90 days, while that for pubertal/postpubertal subjects could be a maximum of approximately 270 (3 separate

active periods of approximately 90 days for those treated with icatibant during an attack), with each active period separated by periods of inactive participation of variable duration. The period of active participation may be shorter if pubertal/postpubertal subjects have recurrent HAE attacks in between the Day 8 and Day 90 visits for a prior icatibant-treated HAE attack. Telephone follow-up will occur approximately 6 months after each initial icatibant-treated attack.

Once the tenth prepubertal subject and the twentieth pubertal/postpubertal subject have completed the 6-month follow-up after the initial treatment, and the tenth pubertal/postpubertal subject has completed the Day 90 follow-up after his or her third and final treatment for an attack, the study will be closed.

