8.3.3 Follow-up Visit (Day 90 \pm 7 days)

In the event that a subject has a subsequent HAE attack within the 90 day follow-up period for the first treatment, the date of the Day 90 follow-up visit for the first treatment remains the same. Each subsequent treatment will have a corresponding Day 90 follow-up visit.

- Physical examination
- Vital signs
- Height and weight
- Clinical laboratory tests (serum chemistry, hematology, and urinalysis)
- Urine pregnancy test (in females of childbearing potential)
- Reproductive hormone assessments
- Immunogenicity evaluation
- Menstrual cycle history (in pubertal/postpubertal females)
- Recording of concomitant medications
- Assessment of AEs
- Documentation of HAE attack(s) not treated with icatibant

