8.4.3 Follow-up Visits

Each treatment for a subsequent attack will require a Day 8 and a Day 90 follow up visit. If a subsequent attack occurs within 3 days of the Day 8 follow-up visit for the previous attack, the visits for Day 1 (of the subsequent icatibant-treated attack) and Day 8 (of the prior icatibant-treated attack) will be combined. If a subsequent attack occurs within 7 days of the Day 90 follow-up visit for the previous attack, the visits for Day 8 (of the subsequent icatibant-treated attack) and Day 90 (of the prior icatibant-treated attack) will be combined.

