### 7.9 Safety Analyses

All safety summaries will be presented by icatibant exposure number, if not otherwise specified. For the initial icatibant exposure, the analyses will be presented by the pubertal status and overall; for the subsequent icatibant exposures, the analyses will be presented by the administration type (HCP Administration vs. Caregiver Administration) and overall.

All safety summaries will be presented for the initial icatibant exposure and both subsequent icatibant exposures.

All safety outcomes will be listed by subject.

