#### 10.2.11 Attribution of AEs

For subjects treated with study drug for more than one attack during the study, adverse events will be programmatically assigned to the appropriate attack by comparing the reported dates and times of first study drug administration for all attacks with that of AE onset. Events will be assigned to the latest attack for which the study drug administration preceded the AE onset. If the adverse event start time is missing, but the adverse event start date is the same as a dosing date, then the adverse event will be attributed to the attack that was dosed on that day.

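### Exposure-1 and exposure-2 Day 90 samples, and exposure-2 Day 8 samples, can be taken after the next dose yet are tabulated unflagged under the earlier exposure

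*SAP*

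**What the plan says.** Protocol 4.1.3.2 offers further treatment to pubertal/postpubertal subjects "who present subsequently with an attack at least 3 days after prior treatment", and Protocol 6.2 caps the total at three doses. Prepubertal subjects receive one.

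Overlap between exposures is foreseen. Protocol 4.3 mentions "recurrent HAE attacks in between the Day 8 and Day 90 visits for a prior icatibant-treated HAE attack". Protocol 8.3.3 states that, if a new attack falls in the first 90 days, "the date of the Day 90 follow-up visit for the first treatment remains the same". Protocol 8.4.3 gives each later treatment its own Day 8 and Day 90 visits, with one merge for late redosing: "If a subsequent attack occurs within 7 days of the Day 90 follow-up visit for the previous attack", then "the visits for Day 8 (of the subsequent icatibant-treated attack) and Day 90 (of the prior icatibant-treated attack) will be combined". A second merge joins Day 1 of the new attack to Day 8 of the prior one when the attack is within 3 days of that Day 8 visit.

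On analysis, SAP 7.9 states: "All safety summaries will be presented by icatibant exposure number, if not otherwise specified". SAP 10.2.13, which concerns antibodies only, says that "immunogenicity data supporting two combined visits will be programmatically copied to both visits". Its Baseline paragraph takes the last baseline value before the post-baseline sample, whatever the date of the dose. For adverse events, SAP 10.2.11 says: "Events will be assigned to the latest attack for which the study drug administration preceded the AE onset".

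**The concern.** Antibodies and reproductive hormones are part of the primary safety endpoint (SAP 5), and the objectives separate the hormone effect of a single dose (SAP 3.1) from that of repeated exposures (SAP 3.2). If an exposure-1 Day 90 value was drawn after a second dose, the exposure-1 row is not a single-exposure result for that subject. An adverse event starting on the same day would be counted under exposure 2. The copy rule does this explicitly for merged antibody visits. For everything else the SAP is silent, and tabulation by nominal visit gives the same result.

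The affected cells are:
- Day 90 of exposures 1 and 2: antibodies, hormones, vital signs and the scheduled laboratory tests.
- Day 8 of exposure 2: antibodies, hormones and vital signs. Protocol 8.4.3.1 lists no laboratory tests there.

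Exposure 3 and prepubertal subjects cannot be affected.

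**Working it through.** The plan has no figure of its own to reproduce: the sample size is stated to be empirical (Protocol 10.2), and overlapping visits are not counted anywhere. The check is date arithmetic.

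**Inputs**
- Study day = date − dose date + 1 (SAP 10.2.5). Day 8 (±1) is therefore 6-8 days after the dose, nominally 7; Day 90 (±7) is 82-96 days after, nominally 89.
- Minimum gap between doses: 3 days in the current text. The summary of changes for Amendment 4 shows that it was 7 days before. Protocol 1.2.2, in that same amendment, reports the initial treatment part as complete. I therefore use 7 days for exposure 1 and 3 days for exposure 2. The latter is the widest case, since an exposure-2 gap before the amendment also had the 7-day minimum.
- Merge windows: 7 days before Day 90 and 3 days before Day 8 (Protocol 8.4.3).
- Denominators: at least 20 pubertal/postpubertal subjects and 30 in all at exposure 1 (Protocol 10.2); at least 10 subjects with three treatments (Protocol 4.1.3.2).

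**Day 90.** Let g be whole days from dose n to dose n+1. The nominal Day 90 sample follows dose n+1 when g ≤ 88. It is merged when 89 − g ≤ 7, so g = 82 to 88, which is 7 values.
- Exposure 1: g = 7 to 88, or 88 − 7 + 1 = 82 values; 82 − 7 = 75 unmerged (75/82 = 91.5%).
- Exposure 2: g = 3 to 88, or 86 values; 86 − 7 = 79 unmerged (79/86 = 91.9%).
- With the visit at 82 or 96 days instead: exposure 1, 68/75 = 90.7% and 82/89 = 92.1%; exposure 2, 72/79 = 91.1% and 86/93 = 92.5%.

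**Time since the later dose.** A merged sample is that dose's Day 8 sample, 6-8 days after it. The merged visit falls g + 6 to g + 8 = 88 to 96 days after dose n, always inside the Day 90 window. An unmerged Day 90 sample is 89 − 81 = 8 days after dose n+1 at the least, and 89 − 7 = 82 (exposure 1) or 89 − 3 = 86 (exposure 2) at the most.

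**Example.** Dose 2 is given 40 days after dose 1. The exposure-1 Day 90 sample at 89 days is 89 − 40 = 49 days after dose 2. It stays under exposure 1; an adverse event starting that day goes to exposure 2.

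**Exposure-2 Day 8.** At 7 days after dose 2, the visit follows dose 3 when g = 3 to 6. For g = 4 to 6 it is merged with Day 1 (7 − g ≤ 3). The pre-dose steps in Protocol 8.4.2.1 include no blood sampling or vital signs, so it is not stated whether the Day 8 sample precedes dose 3. For g = 3 it is unmerged and drawn 7 − 3 = 4 days after dose 3.

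**Effect on an antibody rate.** One extra positive moves the exposure-2 overall rate by 1/10 = 10 points at its minimum n. For exposure 1 it moves the rate by 1/20 = 5 points (pubertal/postpubertal) or 1/30 = 3.3 points (overall). For scale, exact 95% intervals are 0-30.8% for 0/10 and 0.25-44.5% for 1/10; 0-16.8% for 0/20 and 0.13-24.9% for 1/20.

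**Share of subjects.** The documents give no attack rate. Assuming 1, 4 or 12 treated attacks a year at a constant rate, 1 − exp(−rate × 86/365.25) gives 21%, 61% or 94% redosed between days 3 and 89. The range is too wide to settle anything, and the conclusion does not use it.

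**Antibody baseline (secondary).** The baseline must precede the post-baseline sample, not the dose, so a six-monthly sample drawn after the dose can serve as baseline. Positivity in SAP 7.9.3 does not use the baseline value. A by-exposure count falls only if the subject is positive at that visit and negative at the same exposure's Day 8 and Day 90.

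**The case against.** The best defence is that this is convention. Scheduled samples are commonly tabulated by nominal visit and adverse events by latest dose; different rules for different data types are not a contradiction. The harm is also limited. SAP 7.9.3 adds an analysis of all antibody measurements, every safety outcome is listed by subject, no formal testing is planned (SAP 9.3), and prepubertal exposure-1 results are shown separately. An adult half-life of 1.4 hours (Protocol 1.2.1) makes a direct drug effect days later unlikely.

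Most of this stands and sets the grade. It does not remove the point. The all-measurements analysis covers antibodies only; the hormone, vital-sign and laboratory tables in SAP Appendix I are by exposure alone. A reader of the listings would have to work out attribution unaided.

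Four stronger readings are tempting but unsupported:
- From the 3-day interval, a reader might infer that exposure-1 Day 8 samples are also affected, even by several doses within the first week. The initial treatment part was already complete when that interval came in. The preceding text let a Day 8 assessment in that window serve as pretreatment for the next attack.
- A reader might take the unmerged share, about 92%, as a share of patients or visits. It counts possible calendar days.
- A reader might conclude that exposures 2 and 3 have no pretreatment sample. SAP 10.3.3 schedules a baseline visit with antibodies, hormones, vital signs and laboratory tests, to be done within 6 months before treatment.
- A reader might treat six-monthly visits as falling at random relative to doses and so expect the baseline problem often. Footnote a of that schedule ties a repeat baseline visit to the absence of further attacks.

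**Conclusion.** The concern holds, as a minor point about descriptive tables. In redosed pubertal/postpubertal subjects, the exposure-1 and exposure-2 Day 90 summaries and the exposure-2 Day 8 summaries can contain values taken after the next dose. The copy rule does so by design for merged antibody visits; all other cases have no rule.

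The 10-point shift applies only to exposure 2 at n=10. Copying adds a positive to the earlier exposure and takes none from the later one. The antibody-baseline wording is a real slip with a small effect.

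This rests on three assumptions: unmerged samples are tabulated by nominal exposure and visit, as SAP 7.9 implies; the 7-day minimum governed redosing after exposure 1; and at least some subjects were redosed before Day 90, which the protocol foresees but does not quantify.

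**What to change.** 1. In SAP 10.2.13, for antibodies, hormones, vital signs and laboratory tests, flag and list every exposure-n value taken after dose n+1. Include results copied under Combined Visits, and values on the date of dose n+1 with no recorded time. Show the exposure-1 Day 90, exposure-2 Day 90 and exposure-2 Day 8 summaries with and without flagged values, for the tests actually scheduled (no exposure-2 Day 8 laboratory tests, and no urinalysis after subsequent attacks).
2. Redefine the antibody baseline for exposure n as the last non-missing value from a scheduled baseline visit before the date and time of dose n, and use the same definition for the other three data types. Fall back on a follow-up value from exposure n−1 only when no such baseline exists, and list it as such. This order keeps a post-dose follow-up value from displacing a scheduled baseline.

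The cost is SAP wording, derivation code and some additional summaries, with no new data or visits. The drawback is fewer values in the restricted summaries, which are already small.

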#### **Baseline**

The baseline measurements for immunogenicity data for the subsequent exposures were collected every six months, regardless of the dates of icatibant exposures. Therefore, the last non-missing baseline immunogenicity measurement that was prior to a post-baseline measurement will be considered as the baseline measurement for that post-baseline measurement.

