8.4.1 Subsequent Icatibant-treated Attack Baseline Assessments

All evaluations and sample collections must be performed at the hospital/study center within 6 months prior to treatment:

- Confirm inclusion/exclusion criteria
- Menstrual cycle history (in pubertal/postpubertal females only)
- Documentation of HAE attack(s) not treated with icatibant
- Physical examination
- Vital signs
- Height and weight
- Clinical laboratory tests (serum chemistry and hematology)
- Urine pregnancy test (in females of childbearing potential)
- Reproductive hormone assessments
- Immunogenicity evaluation
- Recording of concomitant medications
- Assessment of AEs
- Training for parent/legal guardian/caregiver on how to assess HAE symptoms using the 5-point rating scale, time to initial symptom relief, and injection site reactions (for subjects who have expressed interest in self-administering or having a parent/legal guardian/caregiver administer icatibant in the home)
- Training on icatibant administration (for subjects who have expressed interest in self-administration or having a parent/legal guardian/caregiver administer icatibant in the home)
- Dispense 1 syringe of study drug (for subjects who have expressed interest in being treated at home by a home healthcare provider, parent/legal guardian/caregiver, or self-administration)
- Instruct the subject (parent/legal guardian/caregiver) to record a weight measurement every month and to contact the hospital/study center to confirm dosing (for subjects who have expressed interest in being treated at home by a home healthcare provider, parent/legal guardian/caregiver, or self-administration)

- Instruct the subject (parent/legal guardian/caregiver) to contact the hospital/study center (or their home healthcare professional in the event the investigator is not available) at the time of a subsequent attack to confirm the HAE attack diagnosis.

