^a All evaluations and sample collections must be performed at the hospital/study center within 6 months prior to treatment if a repeat attack does not occur within 6 months. If a second “baseline” visit is conducted due to lack of repeat attacks, one of the monthly phone calls may overlap with the onsite visit. In this case, a monthly call would not be necessary.

^b These assessments may be conducted by telephone contact.

^c If a subsequent attack occurs within 3 days of the Day 8 follow-up visit for the previous attack, the visits for Day 1 (of the subsequent icatibant-treated attack) and Day 8 (of the prior icatibant-treated attack) will be combined. If a subsequent attack occurs within 7 days of the Day 90 follow-up visit for the previous attack, the visits for Day 8 (of the subsequent icatibant-treated attack) and Day 90 (of the prior icatibant-treated attack) will be combined.

^d For subjects who have expressed an interest in self-administering or having a parent/legal guardian/caregiver administer icatibant in the home.

^e For subsequent attacks, study drug may be administered by study site personnel at the hospital/study center or by qualified home healthcare personnel at the subject’s home. Alternatively, a parent/legal guardian/caregiver will be allowed to administer or the subject (under the supervision of a parent/legal guardian/caregiver) will be allowed to self-administer the investigational product after having received appropriate training. For all subsequent laryngeal attacks, subjects should be advised to seek medical attention in an appropriate healthcare facility immediately following treatment with icatibant.

^f If after the completion of the assessments scheduled for 2 hours post-treatment, the subject’s pain is absent, no further Day 1 assessments are required. If the subject’s pain at 2 hours post-treatment is NOT absent, the subject will be assessed every 2 hours until pain is absent.

^g For subjects treated at the hospital/study center only.

^h The subject will be observed for a minimum of 2 hours after icatibant administration. If after the completion of the assessments scheduled for 2 hours post-treatment, the subject’s symptoms are absent or mild, no further Day 1 assessments are required. If the subject’s symptoms at 2 hours post-treatment are moderate, severe, or very severe, the subject will be assessed every 2 hours until the subject’s symptoms are absent or mild.

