### 7.9.3 Immunogenicity

Serum samples for immunogenicity testing for determination of anti-icatibant antibodies will be collected pre-treatment and 8 and 90 days post-treatment. A subject will be considered as anti-icatibant antibody positive if he/she has at least 1 positive antibody result after the pre-treatment visit.

The number and percentage of subjects with a positive post-treatment antibody test result will be summarized.

For analyses on immunogenicity, in addition to summaries by icatibant exposure number, the analyses on all immunogenicity measurements by pubertal status stratification level and overall will be performed as well.

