### 7.9.7 Reproductive Hormone Assessments

Reproductive hormone levels will be measured in all subjects at pre-treatment, and 6 hours, 8 days and 90 days post-treatment for the initial icatibant treatment, and pretreatment, 8 days and 90 days post-treatment for subsequent icatibant-treated attacks. FSH, LH, estradiol, and progesterone will be summarized for females, and FSH, LH, and testosterone will be summarized for males. Observed values and changes from pre-treatment will be summarized by study time-point. The number and percentage of subjects with levels outside the normal range defined for their sex and pubertal status will be summarized by study time-point. Observations below the limit of detection will be considered abnormal if the lower limit of normal is not zero.

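### The antibody baseline for exposures 2 and 3 is tied to the follow-up sample, not the dose, and no rule selects the hormone, laboratory or vital-sign baselines

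*SAP*

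**What the plan says.** At the first exposure, hormones, antibody, laboratory tests and vital signs are all taken on Day 1 before dosing (Protocol 8.2.1 and 8.3.1).

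For exposures 2 and 3 they move to a separate site visit. Protocol 8.4.1 requires that "All evaluations and sample collections must be performed at the hospital/study center within 6 months prior to treatment". Protocol 4.1.3.2 adds, for subjects enrolled longer than 6 months, that "a study visit will be scheduled every 6 months to collect baseline information". Footnote a of Protocol Appendix 3 words the timing differently: "within 6 months prior to treatment if a repeat attack does not occur within 6 months". It then describes a second baseline visit as one held because no repeat attack has occurred.

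On the day of a repeat attack, Protocol 8.4.2.1 and Appendix 3 list symptom and pain scores, a urine pregnancy test, concomitant medications and adverse events before dosing. They list no blood sample and no vital signs.

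SAP 7.9.7 schedules hormones at "pretreatment, 8 days and 90 days post-treatment for subsequent icatibant-treated attacks" and summarises change from pre-treatment. SAP 7.9.6 does the same for vital signs, and Tables 14.3.8.2 and 14.3.9.2 do so for chemistry and hematology. None of these places says which sample is the pre-treatment value for exposures 2 and 3.

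For antibody there is a rule. SAP 10.2.13 states: "The baseline measurements for immunogenicity data for the subsequent exposures were collected every six months, regardless of the dates of icatibant exposures". It concludes that "the last non-missing baseline immunogenicity measurement that was prior to a post-baseline measurement will be considered as the baseline measurement". SAP 7.9.3 calls a subject positive "if he/she has at least 1 positive antibody result after the pre-treatment visit".

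**The concern.** A baseline should describe the subject before the dose under study. The antibody rule does not require that. It takes the latest baseline-visit sample before each follow-up sample, so a visit held after the dose can supply the baseline. Two samples from one exposure can then have different baselines. A response that appears and fades between Day 8 and Day 90 can be labelled baseline for the dose that may have caused it. Protocol 1.2.2 describes antibody positivity in the earlier Phase III studies as transient, though rare.

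The second problem is the age of the value. The effect of repeated exposure on reproductive hormones is a stated objective (Protocol 2.2). A Day 8 hormone change covers one week at exposure 1. At exposures 2 and 3 it can cover months of puberty and, if the visit predates the previous dose, the effect of that dose too. Protocol 7.6 itself says hormone changes in adolescent females cannot be interpreted without knowing where in the menstrual cycle the sample was drawn.

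**Working it through.** Neither document states a baseline age or an overlap frequency, so there is no figure to reproduce. The check applies the SAP rule to the protocol's calendar.

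**Inputs**
- Baseline visits every 6 months: 365.25/2 = 182.6 days (Protocol 4.1.3.2, SAP 10.2.13).
- Day 8 sample: 7 days after the dose. Day 90 sample: 89 days after, or 82 to 96 with the ±7-day window.
- Repeat dosing is open to subjects who "present subsequently with an attack at least 3 days after prior treatment", so the minimum gap is 3 days.
- Assumed, for the frequencies only: visits strictly six-monthly and dose dates uniform between them.

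**Step 1: one worked calendar.** Baseline visits on days 0 and 183, dose 2 on day 100, dose 3 on day 120.

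| Exposure | Sample | Sample day | Antibody baseline under 10.2.13 | Position |
|---|---|---|---|---|
| 2 | Day 8 | 107 | day 0 | 100 days before dose 2 |
| 2 | Day 90 | 189 | day 183 | 83 days after dose 2 |
| 3 | Day 8 | 127 | day 0 | 120 days before dose 3, and before dose 2 |
| 3 | Day 90 | 209 | day 183 | 63 days after dose 3 |

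Both Day 90 baselines follow the dose, and each exposure has two different baselines. This needs no distributional assumption.

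**Step 2: which antibody results are affected.** Take an antibody negative on Day 8, positive on day 183 and negative on Day 90. The positive sits at a visit designated as baseline, so neither scheduled post-treatment sample of that exposure is positive and 7.9.3 does not count it there. A positive Day 8 or a positive Day 90 would still count, because 7.9.3 needs only one positive and does not require a negative baseline.

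**Step 3: how often a visit could fall between dose and sample.** Share = offset/182.6.
- Day 90: 89/182.6 = 49% (82/182.6 = 45% to 96/182.6 = 53% over the window).
- Day 8: 7/182.6 = 4%.
- Day 8 and Day 90 with different baselines: (89 − 7)/182.6 = 45%.

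**Step 4: age of the last six-monthly value at dosing.** Mean 182.6/2 = 91 days, maximum about 183. A Day 8 change measured from it spans 91 + 7 = 98 days on average and at most 182.6 + 7 = about 190, against 7 days at exposure 1.

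**Step 5: chance that this value precedes the previous dose.** Share = 1 − gap/182.6.
- 3-day gap: 98%
- 30 days: 84%
- 60 days: 67%
- 90 days: 51%
- 180 days: 1%

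**Step 6: effect of a pre-dose rule that admits any visit.** In the calendar of Step 1, the dose 3 baseline moves from day 0 (120 days old, before dose 2) to the exposure 2 Day 8 sample on day 107, which is 120 − 107 = 13 days old. The dose 2 baseline stays at day 0 unless a nearer exposure 1 follow-up sample exists.

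**The case against.** Several points limit the concern, and most of them stand.

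- **Scope of the six-monthly statement.** The sentence saying that collection ignored exposure dates is about immunogenicity only. A reader might infer that hormones, laboratory tests and vital signs follow the same rule. They do not: Protocol 8.4.1 points to a pre-dose value for them, and the SAP is merely silent on which one.
- **Some doses have a close sample.** A reader might infer that no blood is ever drawn near a repeat dose. Protocol 8.4.3 combines Day 1 of a new attack with Day 8 of the previous one when they fall within 3 days, and Day 8 includes vital signs, hormones and antibody.
- **Antibody results are not lost.** SAP 7.9.3 also plans an analysis of all immunogenicity measurements by pubertal group and overall, where a late positive may count, although the table list gives that analysis no separate title. Listing 16.2.8.7 shows every result. The likely harm is attribution to the wrong exposure.
- **Visit overlap may be rarer.** Footnote a can be read as repeating the baseline visit only when no attack occurs. With dosing capped at three, a further baseline visit after dose 3 has no evident purpose. Protocol 4.1.3.2 and SAP 10.2.13 point the other way, so the timing is unsettled.
- **Hormones have other summaries.** SAP 7.9.7 also reports observed values and the share outside ranges specific to sex and pubertal status. These need no baseline. No modelling or formal comparison between exposures is planned.

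None of this changes the wording of 10.2.13, which allows a post-dose baseline on either reading of the visit schedule. Nor does it supply the missing rule for the other measurements.

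**Conclusion.** The point holds in two parts. First, the antibody rule is anchored to the wrong event: it permits a post-dose baseline and two baselines within one exposure, and it can drop from that exposure's count a positive first seen at the intervening visit when Day 8 and Day 90 are negative. Second, for hormones, laboratory tests and vital signs at exposures 2 and 3, the value used may be up to 6 months old and may precede the previous dose, with no stated selection rule and no sensitivity analysis (SAP 9.7).

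The percentages show scale only. They rest on strict six-monthly visits and uniform dose dates. A reader might take 49% as the chance that an antibody response is hidden. It is only the chance that a visit falls between dose and Day 90 sample. Hiding a response from the exposure's count also needs negative Day 8 and Day 90 results, and positivity is described as rare. Nor do the documents support saying that the repeat-exposure hormone objective cannot be assessed. The change-from-baseline summaries are weakened, while the observed values and range-based summaries remain.

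This should be corrected before analysis. It does not undermine the study as a whole.

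**What to change.** - In SAP 10.2.13, define the antibody baseline for each exposure as the last non-missing sample taken before that dose. State that a sample drawn after a dose is never its baseline, and that a positive at any visit after a dose counts as post-treatment.
- Apply the same pre-dose rule in SAP 7.9.4, 7.9.6 and 7.9.7, allowing a nearer pre-dose sample from the Day 8 or Day 90 visit of an earlier exposure.
- For exposures 2 and 3, tabulate days from baseline to dose and whether the baseline precedes the previous dose. The documents offer no basis for a fixed age cut-off, so none is proposed.
- Reconcile Protocol 4.1.3.2 with footnote a of Appendix 3 on when the baseline visit is repeated.

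The cost is SAP wording, one changed derivation and one added table, with no new samples. The drawback is that baselines will come from mixed visit types, some soon after an earlier dose. Where no nearer sample exists, an old baseline stays old. That comes from the visit design, and the SAP can only disclose it.
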